6.3.8. Visits 6-13: Three-monthly maintenance treatment administrations

These visits will take place at 3-month intervals, i.e., at time-points 6, 9, ..., 27 months after Visit 1, with a permitted deviation from the scheduled time-point of up to 14 calendar days.

The following procedures will be performed at each of these visits:

- Physical examination (as at Visit 1, including ECOG performance status and disease assessment).
- A CT scan of the neck, chest and upper abdomen and pelvic CT scan.
- Before administration of study treatment the criteria for permanent stopping or postponement of study treatment (Sections 5.2.1.1 and 5.2.1.2) will be checked; if any of these is met, the patient will either be withdrawn from study treatment or the administration of study treatment will be postponed.
- Recording of (serious) adverse events and pIMD.
- A pregnancy test for females of childbearing potential.
- Recording of concomitant medications.
- Administration of the study treatment.

The following procedures will be performed before the administration of study treatment at Visits 7, 8 and 10:

- Blood samples (10 ml, as described in Section 6.4.2) for humoral immunity assays will be taken.

The following procedures will be performed once every year after Visit 1 (i.e. at Visits 8 and 12):

- Blood sampling (15 ml as described in Section 6.4.2) for haematological and chemical safety assays.

If any of the sixth to twelfth study treatment administrations had to be postponed (refer to Section 5.2.1.1 for criteria for postponement of study treatment), the subsequent Visit should be planned as close as possible to the 3-monthly interval of the original schedule, but with a minimum of 14 days between any two treatment administrations.

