The sample size for this trial is calculated based on the primary immune endpoint of a serologic response to treatment. In a GSK trial using recMAGE-A3 + AS15 ASCI in a similar patient population, the total anti-MAGE-A3 IgG antibody measured at approximately 6 months at the first vaccine of the maintenance phase for the ASCI arm without Poly IC:LC had a geometric mean of about 7,000 and a standard deviation of no more than 0.28 on the log scale. It is anticipated that the ASCI arm with Poly IC:LC will further increase such anti-MAGE-A3 IgG antibody measurement at 6 months to about 10,500 for a 50% enhancement of the effect. Therefore, 20 patients per arm will yield 62% power for such detection of the anti-MAGE-A3 IgG antibody difference between the two arms at a one-sided significance level of 0.05. Power calculations for this trial will be only for the immune primary endpoint, since little toxicity is expected from either of the treatment arms on which to base a power calculation. Table 1 lists the change in power if the standard deviation deviates from the assumed value of 0.28 when everything else is the same. We plan to enroll 20 patients per arm for a total of 40 patients. To account for an approximate 10% loss-to-follow-up rate in this study, up to 44 patients may be enrolled.

The change in power if the standard deviation deviates from the assumed value of 0.28:

Standard Deviation	0.28	0.26	0.24	0.22	0.20
Power	0.62	0.68	0.74	0.80	0.86

A median RFS of about 8 months was observed for similar patients treated without adjuvant therapy. A median RFS of 12 months is expected of patients treated with recMAGE-A3 + AS15 ASCI alone in resected stage IV melanoma. Adding Poly IC:LC to this ASCI regimen might double the median RFS to 24 months. The power calculation shows that 20 patients per arm would have a power of about 61% for detecting such difference in RFS between the two arms with a one-sided type error rate of 0.05, assuming an accrual rate of 2.5 patients per month and a 3-year follow-up after the completion of accrual.

Assuming an accrual rate of 2.5 patients per month, it would take up to 18 months to enroll 44 patients to this trial.

Data Analyses Plan

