Demographic and disease characteristics as well as other baseline variables for all patients randomized will be tabulated and analyzed using the standard descriptive statistics such as frequency and percentage tables for discrete variables and mean, median, SD, range, and interquartiles for continuous variables. These data will be reported by arm and may be further stratified by subgroups, e.g., those patients with favorable/unfavorable gene signature, of interest.

The total anti-MAGE-A3 IgG antibody measured at various time points over the course of treatment will be descriptively reported by arm with the usual summary statistics as well as with plots and confidence intervals (CIs) to discern any time change pattern of interest. Comparisons between the two arms will be on the log scale using the two sample t test. If the normal distribution assumption is violated for log (total anti-MAGE-A3 IgG antibody), then non-parametric Wilcoxon test and/or other transformations such as ln and square root will be considered as well.

In order to determine whether recMAGE-A3 + AS15 ASCI +/- poly IC:LC is able to induce a specific T-cell response to the MAGE-A3 protein and to evaluate the T-cell response in both treatment groups, the percentage of T-cells simultaneously producing IFN γ and IFN α will be assessed after 5, and after 9 recMAGE-A3 + AS15 ASCI +/- poly IC:LC injections.

The cutoff value for a positive response is defined as 2 standard deviations over the mean percentage of double positive events in control wells. Anti-MAGE-A3 T-cell response is considered as positive when there are at least 3 more positive wells at any point after immunization than at baseline. This variable will be reported using both point estimates and 95% CIs for various subgroups of patients, e.g., arms or patients with favorable/unfavorable gene signature. Antibodies (such as Anti-MAGE-A3) seropositivity status, defined for a patient whose anti-body titer is greater or equal to the cutoff value, will be analyzed similarly.

RFS and OS will be analyzed using the Kaplan-Meier product-limit method as well as the Cox proportional hazards regression models. The Log-rank test for comparing RFS between the two arms will be performed and reported. Confidence interval for the median and survival rates at different time points will be constructed if needed.

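### The 62% power in 10.3 refers to a 6-month titre with no scheduled sample and allows too little for relapse, and 10.7.4 and 10.4.3 disagree on the immunogenicity analysis set

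*Combined protocol and SAP*

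**What the plan says.** **Power.** Section 10.3 bases the sample size on IgG "measured at approximately 6 months at the first vaccine of the maintenance phase", with "a standard deviation of no more than 0.28 on the log scale" and a rise in geometric mean from about 7,000 to about 10,500. It concludes that "20 patients per arm will yield 62% power for such detection of the anti-MAGE-A3 IgG antibody difference", one-sided at 0.05, and tabulates power from 0.62 to 0.86 as the SD falls from 0.28 to 0.20. The test is set out under the data analysis plan in 10.3: "Comparisons between the two arms will be on the log scale using the two sample t test". For attrition: "To account for an approximate 10% loss-to-follow-up rate in this study, up to 44 patients may be enrolled". Section 4.1 calls the same 10% withdrawal from the study.

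**RFS.** The same section states: "A median RFS of 12 months is expected of patients treated with recMAGE-A3 + AS15 ASCI alone in resected stage IV melanoma". It continues: "Adding Poly IC:LC to this ASCI regimen might double the median RFS to 24 months".

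**Sampling.** For the maintenance phase, 6.3.8 introduces the humoral blood draw with "The following procedures will be performed before the administration of study treatment at Visits 7, 8 and 10". Tables 5, 6 and 8 place humoral samples at Visits 1, 3, 5, 7, 8, 10 and 14, and Tables 7 and 8 add follow-up visit F2.

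**Relapse.** Relapse ends study treatment (5.2.1.2) and the regular visit schedule (6.3.10.2). Withdrawn patients are not replaced (9.2), and patients with a missing titre are left out of the analysis (10.6.2).

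**Analysis set.** Section 10.7.4 runs the immunogenicity analysis on the ATP population and refers to 10.4.3. Section 10.4.3 describes an eligible-only analysis as secondary and at the discretion of the PI and biostatistician. It also allows subanalyses that exclude major deviations, with early discontinuation of treatment as an example.

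**The concern.** The visit to which the power statement belongs is the start of maintenance: Visit 6, week 24. A pre-dose draw there would come after five doses, but 10.1.2 and 10.7.4 list draws after 2, 4, 6, 7 and 9 doses. The omission therefore appears in the text as well as in the tables, and is not a damaged table row.

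The loss allowance also sits beside RFS assumptions that imply more than twice that loss by week 24. If the titre comparison is not significant, readers will judge it against 62% power at a visit without planned data.

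The analysis-set conflict touches a primary endpoint in an open-label trial. Nothing says whether stopping because of relapse, which the protocol requires, counts as early discontinuation. If it did, the set would be selected on an outcome that the plan itself expects to differ between arms.

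**Working it through.** **1. Reproduce the plan's figure.** Inputs from 10.3: 20 per arm, SD 0.28, ratio 10,500/7,000 = 1.5, one-sided 0.05, two-sample t test. On the log10 scale the difference is log10(1.5) = 0.1761.

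Noncentrality = 0.1761 / (0.28 × √(1/20 + 1/20)) = 1.989. With 38 df the critical value is 1.686 and power is **0.621**. For SD 0.26, 0.24, 0.22 and 0.20 the results are 0.677, 0.737, 0.800 and 0.862. All five tabulated values match, so the method and the arithmetic are right. Natural logs (above 0.99) and a two-sided test (0.49) do not fit.

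**2. Relapse implied by 10.3.** Assume exponential RFS, S(t) = 2^(−t/median), with weeks converted to calendar months (week 24 = 24 × 7/30.44 = 5.52 months).

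| Week | S, ASCI alone | S, combination | Relapsed or dead of 44 (22 per arm) |
|---|---|---|---|
| 12 | 0.853 | 0.923 | 3.2 + 1.7 = 4.9 |
| 24 | 0.727 | 0.853 | 6.0 + 3.2 = 9.2 |
| 36 | 0.620 | 0.787 | 8.4 + 4.7 = 13.0 (unrounded sum) |

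The allowance is 44 − 40 = 4.

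**3. Power if no relapsed patient has a usable titre.** Same formula, SD 0.28, 1.5-fold effect, no other loss.

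| Visit | Titres from 20 per arm | Power | Titres from 22 per arm | Power |
|---|---|---|---|---|
| Week 24, had titres been drawn | 14.5 + 17.1 | 0.530 | 16.0 + 18.8 | 0.565 |
| Week 36 (Visit 7) | 12.4 + 15.7 | 0.487 | 13.6 + 17.3 | 0.521 |

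**4. Power if only relapses up to the preceding scheduled scan are lost.** A relapse found at a visit triggers the Visit 14 procedures, which include a humoral sample (6.3.12, 6.3.9, Table 6 note a).

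- Week 24, preceding scan at week 12: 17.1 + 18.5 titres give 0.575; 18.8 + 20.3 give 0.611.
- Visit 7, preceding scan at week 24: the step 3 week-24 numbers apply, 0.530 and 0.565.

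**5. Sensitivity of step 3** (20 and 22 per arm).

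- Both medians 12 months: 0.503 and 0.537 at week 24; 0.450 and 0.481 at week 36.
- A further 10% loss from other causes: 0.493 and 0.527; 0.453 and 0.484.
- SD 0.20: 0.778 and 0.813; 0.730 and 0.767, against the plan's 0.86.

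**6. Analysis set, side by side.** Section 10.4.2 defines the Total Treated Population as the set for the trial's data analysis. Section 10.4.3, whose heading names immunogenicity, describes optional additions to that primary analysis. Section 10.7.4 gives the ATP set as the only one for immunogenicity. The three cannot all hold for a primary endpoint.

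**The case against.** **Relapsed patients are not all lost.** Section 6.3.12 requires the Visit 14 procedures when recurrence is found at a scheduled or unscheduled visit, so a relapse seen on the week-24 scan still yields a titre at about that time. This stands, and is why step 4 is needed: with respect to relapse sampling, the step 3 figures are lower limits. How much is recovered is uncertain. Neither 10.6.2 nor 10.7.4 says to which time point such a sample belongs. Table 6 shows the Visit 7 CT only if clinically indicated, while 6.3.8 lists CT at every maintenance visit; these passages need reconciling.

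**The change is small beside the plan's own range.** The plan states a modest 62%, calls 0.28 an upper limit for the SD, and shows power up to 0.86. Planned confidence intervals also reduce the risk of misreading a null result. This is fair and limits the weight of the point, but it does not supply a week-24 sample.

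**The Visit 7 figures carry the SD and effect to week 36.** Correct: the documents do not support this, so it is an assumption.

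**The ATP set may lose nobody through relapse.** Stopping at relapse is required by 5.2.1.2, and relapse is not among the criteria in 10.5. Since 10.4.2 already restricts the treated set to eligible patients, an eligible-only ATP set would largely coincide with it. This is a good argument against assuming a large loss, but it leaves the contradiction on which set is primary.

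**Conclusion.** The point holds as a correction to a stated figure and to conflicting wording. Power is about 0.53-0.57 at week 24, had titres been drawn, and 0.49-0.52 at Visit 7 if no relapsed patient has a usable titre. The upper limits are about 0.58-0.61 and 0.53-0.57 if only relapses by the preceding scheduled scan are lost. All rest on exponential RFS at the plan's medians, SD 0.28, an unchanged 1.5-fold effect, no other loss and 20 to 22 randomised per arm. A smaller SD raises every figure. At the upper end, week-24 power is close to the stated 62%.

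Three stronger readings are not supported:

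- A reader might infer that the 62% was miscalculated. It reproduces exactly; what fails is the visit and the number of titres assumed.
- A reader might infer that the ATP set will shrink to the few patients who finish treatment. Nothing in the documents says that protocol-required stopping for relapse is an exclusion. The fault is that the matter is left open.
- A reader might infer that the non-responder rule in 10.4.2 scores patients without a titre as antibody failures. Section 10.6.2 excludes missing measurements and 10.4.3 rules out imputation, so that reading is unlikely, and it would not affect the t test on log titre.

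This should be fixed, but it does not invalidate the trial.

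**What to change.** **Section 10.3.** Tie the powered comparison to a visit with a scheduled humoral sample, for example Visit 7. A Visit 6 draw can no longer be added, since 6.4.2 ends immunology collection on October 1, 2015 and this version is dated October 28, 2015. Choose the visit without reference to titres by arm and record it as a late choice. Restate the expected number of titres and give power as a range, with the RFS, SD, effect and relapse-sample assumptions shown.

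**Section 10.7.4.** Make the primary immunogenicity set all treated patients, analysed as randomised, who have a titre at the visit. Keep ATP as a sensitivity analysis.

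**Section 10.4.3.** State whether stopping for relapse is a reason for exclusion.

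**Cost.** Wording only: no extra patients, visits or samples. The stated power becomes less favourable, and the visit is named after sampling ended in an open-label trial, which must be disclosed.

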5.3.2. Randomization

Randomization will take place when it has been ascertained that the patient is fully eligible and at most 1 week before administration of the first injection of the study product, which will take place a maximum of 12 weeks after surgery.

Randomization of patients and treatment allocation at the investigator site will be performed utilizing the Moffitt Cancer Center's Subject Registration and Randomization Server, a web-based interactive randomization system (available 24H/day, 7D/week). It will be open-label and stratified on the following variables:

1. M Stage of the disease (M1a vs. M1b vs. M1c)
2. Prior treatment with IFN or anti-CTLA-4 (Yes or No)

The list of randomization numbers will be generated by the study statistician and passed on to Moffitt Research IT at MCC to be programmed in the automated web-based randomization system for this specific trial.

Randomization will be performed a maximum of 1 week before the first study treatment administration, which is assigned as Visit 1. Figure 3 presents the timeline for obtainment of patients' informed consent and the procedures to be performed before the beginning of the study.

After having verified that the patient is fully eligible and having obtained the patient's informed consent to participate in the study, the person in charge of the treatment administration will access the randomization system on Internet. Upon providing a patient number and the stage, and prior treatment with IFN or anti-CTLA-4, the randomization system will use the stratified randomization method to determine the treatment number to be used for the patient.

The actual treatment number used for each treatment administration of the patient must be recorded in the CRF. As soon as the targeted number of randomized patients has been reached, the enrollment of patients will be frozen. However, to allow patients at the screening phase or those who have signed the informed consent form at the time of enrollment hold to be enrolled, an over-enrollment of 5% (4 patients) will be allowed.

[figure not shown]

Figure 3. Timelines for pre-study procedures and obtaining informed consent.

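### The titre comparison behind the sample size uses neither the randomisation strata nor the Visit 1 titre; adjusting for them at a named, sampled visit is a cheap gain if they are prognostic

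*Combined protocol and SAP*

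**What the plan says.** The sample-size part of Section 10.3 states that "20 patients per arm will yield 62% power for such detection of the anti-MAGE-A3 IgG antibody difference between the two arms", at a one-sided level of 0.05. It assumes geometric means of about 7,000 and 10,500 and "a standard deviation of no more than 0.28 on the log scale". The titre in question is the one "measured at approximately 6 months at the first vaccine of the maintenance phase".

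The data-analysis part of Section 10.3 gives the test: "Comparisons between the two arms will be on the log scale using the two sample t test". If log titres look non-normal, a "non-parametric Wilcoxon test and/or other transformations such as ln and square root will be considered as well". No visit is singled out; total IgG "measured at various time points over the course of treatment will be descriptively reported by arm". Section 10.7.4 adds geometric mean titres, seropositivity and antibody response, again without covariates.

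On randomisation, Section 5.3.2 says: "It will be open-label and stratified on the following variables", namely M stage (three levels) and prior IFN or anti-CTLA-4 (two levels). Section 6.3.3 and Table 8 require a titre before the first dose. For RFS, a secondary endpoint, Section 10.7.3.1.1 makes an adjusted Cox model the primary analysis.

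Antibody samples are scheduled at Visits 1, 3, 5, 7, 8, 10, 14 and F2 (Table 8; Section 6.3.8 and Tables 5 to 7 agree). Sections 10.1.2 and 10.7.4 list assessments after 2, 4, 6, 7 and 9 doses. Table 6 puts the first maintenance dose at Visit 6, week 24, which follows five doses. None of the listed samples is at that visit.

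**The concern.** Stratified randomisation balances the arms on the strata. If the strata predict titre, the difference in means varies less than the pooled SD in an unadjusted t test implies. The test is then conservative and its interval too wide. The Visit 1 titre is not balanced by design, so leaving it out costs only efficiency.

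This matters because power is only 62% at the SD used for sizing, enrolment is capped at 44, and Section 6.4.2 ended immunology sampling on October 1, 2015. Power can no longer be bought with more samples, whereas a model uses data already collected. Any such model needs a visit, and the plan does not give a usable one.

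**Working it through.** **1. The plan's own figure.** Inputs from Section 10.3: 20 per arm, means 7,000 and 10,500, SD 0.28, one-sided 0.05.

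- Difference: log10(10,500/7,000) = log10(1.5) = 0.1761.
- Standard error: 0.28 × √(2/20) = 0.0885.
- Noncentrality: 0.1761/0.0885 = 1.99, with 38 degrees of freedom.
- Power by the noncentral t: 0.621. For SD 0.26, 0.24, 0.22 and 0.20 it is 0.677, 0.737, 0.800 and 0.862.

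All five match the plan's table (0.62, 0.68, 0.74, 0.80, 0.86). A two-sided test would give 0.491 and a natural-log SD 0.998, so the plan used a one-sided test on log10.

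**2. The adjusted model by formula.** Regress log10 titre on arm, M stage (2 df), prior therapy (1 df) and Visit 1 titre (1 df). The residual SD is 0.28 × √(1 − R²) and the degrees of freedom are 40 − 6 = 34. With covariates perfectly balanced, power at R² 0, 0.1, 0.2 and 0.3 is 0.620, 0.659, 0.703 and 0.753. Chance imbalance lowers these, so simulation is the fairer guide.

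**3. Simulation.** The documents give no R², block size or stratum mix. Assumed: M stage 40/30/30%, prior therapy 30%, permuted blocks of 4 within strata. There were 20,000 runs per cell (Monte Carlo error about 0.35 points for power, 0.15 for size). With 40 analysed, SD 0.28 and only the strata prognostic:

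| Strata R² | Power, t test | Power, adjusted | Size, t test | Size, adjusted |
|---|---|---|---|---|
| 0 | 0.619 | 0.603 | 0.052 | 0.052 |
| 0.05 | 0.620 | 0.622 | 0.046 | 0.051 |
| 0.1 | 0.628 | 0.648 | 0.042 | 0.048 |
| 0.2 | 0.630 | 0.690 | 0.036 | 0.050 |
| 0.3 | 0.631 | 0.734 | 0.028 | 0.050 |

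The mean 95% interval half-width (log10), t test against adjusted, is 0.178 and 0.183 at R² 0, and 0.179 and 0.153 at R² 0.3.

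- *Smaller SD.* At R² 0/0.1/0.2/0.3 the change in power is −1.7/+1.3/+4.6/+8.4 points at SD 0.24 and −1.5/+0.7/+2.8/+4.5 at SD 0.20.
- *Only the Visit 1 titre prognostic, SD 0.28.* At R² 0.1/0.2/0.3: 0.622 and 0.643, 0.613 and 0.680, 0.618 and 0.732. The t test keeps its size (4.8% and 5.3% at R² 0.1 and 0.3).
- *Discount for the cut-off.* If 80%, 90% or 95% start below it and are coded at half its value, the Visit 1 titre keeps about 52%, 35% or 22% of its R². At R² 0.3 with 90% below, the gain falls from about 11 points to about 1.5.
- *Other assumptions (10,000 runs).* Blocks of 2 and 6 at R² 0.2: 0.625 and 0.684, 0.630 and 0.683. M stage 60/25/15% with prior therapy 50%, R² 0/0.2/0.3: 0.616 and 0.596, 0.627 and 0.681, 0.634 and 0.740.

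**4. How many would be analysed.** Relapse stops treatment (Section 5.2.1.2) and missing titres are excluded (Section 10.6.2). Section 10.3 says: "A median RFS of 12 months is expected of patients treated with recMAGE-A3 + AS15 ASCI alone", and 24 months with Poly IC:LC. Assuming exponential times, the relapse-free share is 0.5^(t/median), with week 12 = 2.76 months and week 36 = 8.28 months. Per arm, 22 × 0.9 = 19.8 remain after 10% loss.

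- Visit 5, week 12: 19.8 × (0.853 + 0.923) = 35.2.
- Visit 7, week 36: 19.8 × (0.620 + 0.787) = 27.9.

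Power, t test and adjusted, at SD 0.28 with loss taken as random:

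| Strata R² | 35 analysed | 28 analysed |
|---|---|---|
| 0 | 0.568, 0.546 | 0.484, 0.450 |
| 0.1 | 0.579, 0.590 | 0.479, 0.479 |
| 0.2 | 0.572, 0.627 | 0.484, 0.521 |
| 0.3 | 0.571, 0.672 | 0.478, 0.567 |

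**The case against.** The strongest reply is that this is a preference. The t test is valid, it matches the sizing, and a conservative test misleads nobody. Nothing in the documents says that M stage, prior therapy or Visit 1 titre predicts the later titre. Adjusting breaks even only at a strata R² of about 0.05 with 40 analysed and about 0.1 with 28, and loses power below that. The SD of 0.28 is an upper bound, and the gain shrinks at smaller SDs. All of this stands, and it is why the point is optional.

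The counts of 35 and 28 are also rough. The first scheduled on-study CT is at Visit 5, the same visit as the antibody draw, so patients whose relapse that scan finds may still have a titre; 44 × 0.9 gives up to about 40. If relapse is mostly found at the week-24 scan, Visit 7 would have about 31. Loss was simulated as random although the assumed relapse-free shares differ by arm, so nominal size has not been shown for Visit 7.

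Finally, adjustment leaves other matters open. Section 10.1.2 names seropositivity as the primary immune endpoint, and Section 10.4.3 gives p < 0.05 without sidedness while the power is one-sided. This version postdates the end of sampling in an open-label trial, so choosing a visit and a model now carries some selection risk. None of this removes the case for using the strata, or the need to name a visit.

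**Conclusion.** The point holds as an optional efficiency improvement; the stated power is not in error. With 40 analysed and SD 0.28, the adjusted model gains about 2, 6 and 10 points at strata R² 0.1, 0.2 and 0.3, and restores a one-sided size that the t test lets fall to 4.2%, 3.6% and 2.8%. If the covariates explain nothing it costs about 2 points with 40 or 35 analysed and about 3 with 28. The gain rests on assumed R², block size and stratum mix; changing the last two made little difference. The Visit 1 titre contributes little if most patients start below the cut-off. That the powered visit has no scheduled sample needs no assumption: it follows from the plan's own tables.

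**What to change.** Before any between-arm titre comparison, amend Sections 10.3 and 10.7.4:

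1. Name one sampled visit as the primary titre time point. Visit 5 (week 12) and Visit 7 (week 36) bracket the powered six months. Say that 7,000, 10,500 and 0.28 are carried over as assumptions, since the documents give no mean or SD for either visit, and give the number expected to be analysed.
2. Make the primary titre comparison a linear model of log10 titre at that visit on arm, M stage, prior IFN or anti-CTLA-4 (main effects) and Visit 1 log10 titre. Code values below the cut-off at half of it, as Section 10.6.2 does for the geometric mean.
3. Keep the unadjusted t test as a supporting result. Report the Wilcoxon test as a fixed sensitivity analysis rather than switching after a normality check; moving from log10 to ln only rescales the data.

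No change is needed for RFS. The cost is one sentence for the visit, one for the model and 4 degrees of freedom, with no new samples. Choosing the visit is the larger decision: Visit 5 keeps more patients but is sampled after four doses, before maintenance; Visit 7 follows dose 6 but loses more. If a between-arm titre comparison has already been made, report the adjusted result as chosen afterwards.

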2.2. Secondary objectives

- To evaluate the clinical activity of the recMAGE-A3 + AS15 ASCI compared to recMAGE-A3 + AS15 ASCI in combination with Poly IC:LC in terms of relapse-free survival (RFS) and overall survival (OS) in the overall study population.
- To evaluate the immunogenicity of the recMAGE-A3 + AS15 ASCI compared to recMAGE-A3 + AS15 ASCI in combination with Poly IC:LC measured by T cell responses against MAGE-A3.
- To assess the gene profile of tumor tissue in the two study arms and evaluate the activity of the recMAGE-A3 + AS15 ASCI +/- Poly IC:LC in terms of RFS in the sub-population of patients presenting a potentially favorable gene signature (see Section 6.4.4), and in the sub-population of patients without this gene signature.

Refer to section 10.2 for definitions of secondary endpoints.

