10.3. Study design/sample size and power/data analyses

Study Design

This is a 1:1 randomized, two-arm, open-label, Phase II, single-center study to evaluate the safety, tolerability and immunogenicity of recMAGE-A3 + AS15 ASCI with Poly IC:LC as adjuvant therapy compared to recMAGE-A3 + AS15 ASCI alone in MAGE-A3 positive patients with completely resected stage IV melanoma. Secondary objectives include: to describe the efficacy in terms of Relapse-Free Survival (RFS) and Overall Survival (OS) of the two arms; to collect preliminary data on the T cell immune response to the ASCI in the overall study population as well as subsets of patients of interest (e.g., arms and gene signature groups), and to evaluate the gene signature in all patients when possible. The study treatment will consist of an induction phase and a maintenance phase. During the induction phase, immunization with or

without Poly IC:LC will be administered 5 times at 3-week intervals. During the maintenance phase, immunization with recMAGE-A3 + AS15 with or without Poly IC:LC will be administered 8 times at 3-month intervals. The 13 immunizations with or without Poly IC:LC will be administered over a period of 27 months. The total duration of the study treatment phase (including concluding visit) is 30 months per patient. The duration of active follow-up for survival, recurrence and serious adverse events (SAEs) related to the study participation and concurrent GSK medications will be 5 years from the first administration of study treatment.

Sample Size/Power Calculations and Accrual

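### The only summary specified for the T-cell secondary endpoint is a yes/no responder rate; a full-scale comparison of the arms would be a cheap addition

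*Combined protocol and SAP*

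**What the plan says.** The secondary objective in Section 2.2 is comparative: ASCI alone against ASCI "in combination with Poly IC:LC measured by T cell responses against MAGE-A3". The study-design paragraph of Section 10.3 is more modest; there the aim is "to collect preliminary data on the T cell immune response to the ASCI in the overall study population" and in subsets of interest.

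The Data Analyses Plan in Section 10.3 starts from a continuous quantity, the share of T cells producing both cytokines, which "will be assessed after 5, and after 9 recMAGE-A3 + AS15 ASCI +/- poly IC:LC injections". Two rules follow.

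- Well level: "The cutoff value for a positive response is defined as 2 standard deviations over the mean percentage of double positive events in control wells".
- Patient level: the anti-MAGE-A3 T-cell response "is considered as positive when there are at least 3 more positive wells" than at baseline, at any time after immunization.

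The reporting sentence then covers the patient-level result: "This variable will be reported using both point estimates and 95% CIs for various subgroups of patients", with arms and gene-signature groups as examples. Neither Section 10.3 nor Section 10.7.4 specifies a summary or an arm comparison for the percentage or for the number of positive wells. Section 10.7.4 lists antibody measures only. By contrast, Section 10.3 compares the antibody titre between arms on its log scale with a t test, with Wilcoxon as the fallback.

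**The concern.** A patient who gains 3 positive wells counts the same as one who gains 20, and a patient who gains 2 counts as a non-responder. If Poly IC:LC mainly strengthens the response in patients who would respond anyway, the responder rate can be identical in the two arms while the T-cell responses differ. Section 1.2.1 presents better immunogenicity from the added adjuvant as what the trial will determine, so this is information that a small study should keep.

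The rule also accepts a positive result at any time after immunization. Patients who agree to the extra draws on days 1 to 21 after doses 1 and 5 would have more chances to be called positive if those samples feed the rule. The plan does not say whether they do.

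**Working it through.** **Step 1: reproduce the plan's own immune power figure.** Inputs from Section 10.3: geometric means 7,000 and 10,500, SD 0.28 on the log scale, 20 per arm, one-sided 0.05.

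- Difference = log10(10,500/7,000) = log10(1.5) = 0.1761.
- Standardised effect d = 0.1761/0.28 = 0.629.
- Noncentrality = d × √(20/2) = 1.989, with 38 degrees of freedom and critical t = 1.686.
- Power = 0.621, against 0.62 stated. The SD table also reproduces (0.621, 0.677, 0.737, 0.800, 0.862 for SD 0.28 down to 0.20).

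This figure is for the antibody titre. The documents give no effect size, SD, number of wells, test or power for T cells.

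**Step 2: precision of what is planned.** With 10 responders among 20, the exact (Clopper-Pearson) 95% CI is 27% to 73%. For a difference between two such arms, the Wald half-width is 1.96 × √(2 × 0.25/20) = 0.31, or 31 points. Twenty per arm is an upper limit: Section 6.4.2 ends immunology sample collection on October 1, 2015, and Section 10.6.2 excludes missing immunogenicity measurements.

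**Step 3: illustration of what one cut costs.** Assumption: the T-cell effect equals the antibody effect, d = 0.629, on a normal scale. If the control responder rate is p, the experimental rate is Φ(Φ⁻¹(p) + d); for p = 0.50 this is Φ(0.629) = 0.735. Power by exact enumeration, 20 per arm, one-sided 0.05:

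| Control rate | Experimental rate | Chi-square | Fisher | Full-scale t test |
|---|---|---|---|---|
| 0.10 | 0.257 | 0.37 | 0.23 | 0.62 |
| 0.20 | 0.416 | 0.45 | 0.33 | 0.62 |
| 0.35 | 0.596 | 0.44 | 0.32 | 0.62 |
| 0.50 | 0.735 | 0.45 | 0.33 | 0.62 |
| 0.70 | 0.876 | 0.39 | 0.26 | 0.62 |

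With 14 evaluable per arm the t test has 0.49 and chi-square 0.30-0.36. With d = 0.8 and 20 per arm they are 0.80 and 0.52-0.61.

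**Step 4: the well-count rule itself.** This needs invented inputs, so two simulations with different assumptions are shown.

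- Setting A: 5% background positivity, gamma-distributed patient response, and the mean response rate per well multiplied by 2.5-3. It compares Wilcoxon on the change in positive wells with chi-square on the rule. With 24 wells: 0.54-0.72 against 0.41-0.51. With 48 wells: 0.65-0.78 against 0.29-0.40. With 12 wells and a weak response there was no gain: 0.45 against 0.49.
- Setting B: normal well values, with the effect set so that the full-scale comparison has power of about 0.62. A t test on the change in wells had 0.37-0.55 and the rule 0.07-0.41, over 6 to 48 wells.

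The direction is usually the same, but the size depends on inputs that the documents do not contain.

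**The case against.** The strongest reply is that no T-cell test is planned. The endpoint is reported by estimation, the data are called preliminary, and Section 10.3 confines power calculations to the primary immune endpoint (though it also gives a figure for RFS). This stands. A reader might infer from the table that the plan gives up 17 to 25 points of power (0.62 − 0.45 and 0.62 − 0.37). The documents do not support that: there is no stated T-cell power to reduce, the effect is borrowed from the antibody titre, and the figure describes a single cut with one choice of test.

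A reader might also count the well-level threshold as a second avoidable loss. That is not established. Calling a well positive against control wells may be part of the assay read-out, and a comparison of well counts would keep it.

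Third, a yes/no definition suits part of the purpose in Section 10.3, namely whether treatment can induce a specific response at all. The plan also says that the percentage will be assessed, so a by-arm summary is not ruled out. Both points are fair. They are reasons to keep the responder rate, but they do not supply the missing comparison of response size.

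Finally, a fixed-visit analysis loses patients who have no sample at that visit, whereas the any-time rule can still use them. That also stands, and the numbers evaluable must therefore be reported.

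**Conclusion.** The point holds as a cheap improvement to an unpowered secondary endpoint. The only specified T-cell summary discards the size of the response, while Section 2.2 asks for a comparison of the arms and the antibody titre in the same section is compared on its full scale. The certain cost is lost information and wide intervals. The power contrast of 0.62 against 0.37-0.45 (chi-square) or 0.23-0.33 (Fisher) is an illustration. It rests on d = 0.63 carrying over to T cells, 20 evaluable per arm, one-sided 0.05, a single cut and control responder rates of 10-70%. It should not be cited as the plan's loss. With few wells and a weak response the gain can be nil.

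**What to change.** In Section 10.3, add a between-arm comparison of the change from baseline in the number of positive wells, or in the log background-corrected percentage of double-positive cells. Use an unstratified Wilcoxon test, give the Hodges-Lehmann difference with its 95% CI, and report the number evaluable in each arm. Stratifying by the randomisation factors is not practical: 3 × 2 = 6 strata in 40 patients leaves about 40/6/2 ≈ 3 per arm per stratum.

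Name one visit, before the T-cell results are compared by arm, that has a cellular sample scheduled for all patients. After the Visit 1 baseline, Tables 5 and 6 schedule these at Visits 5, 7, 10, 12 and 14. The two read-out times in Section 10.3 do not settle the choice:

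- The draws in the three weeks after dose 5 are only for patients who agree, and the plan does not say whether the Visit 5 leukapheresis comes before or after that dose.
- A read-out after nine doses corresponds to Visit 10 at month 18. With the plan's assumed 12-month median RFS in the control arm and exponential relapse, 0.5^(18/12) = 0.35 of patients would still be relapse-free, about 7 of 20.

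Keep the responder rate and its CI as a supportive summary, and state which samples feed the any-time rule.

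The cost is SAP wording and one extra analysis of data the assay already produces; Section 6.4.2 allows analysis of existing samples to continue. The small downside is a scale less familiar to readers than a responder rate.
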